# = Lowest of the lower ranges and highest of the higher ranges are used. Refer to Appendix 16.1.10.1 for the breakdown.

\* Baseline is defined as the result closest and prior to dose on Day 1.

**Programmer note:** for PT, INR and PT/INR, the pre-dialysis value will be the baseline value for that day and the "change from baseline" will be the fold change from baseline "ie. Post-dialysis / Pre-dialysis.

Program: /AAXXXXX/ECR/sas\_prg/stsas/tab\_PROGRAMNAME.sas DDMMYYYY HH:MM

Tables 14.3.5.2, 14.3.5.4 and 14.3.5.6 will be in the following format:

Table 14.3.5.2 Clinical Laboratory Shift From Baseline - Serum Chemistry (Safety Population)

Laboratory Test (unit)	Dose Level/ Placebo	Time Point	Baseline* L			Baseline* N			Baseline* H		
			L	N	H	L	N	H	L	N	H
XXXXXXX (unit)	XXX <units>	Day X, Hour X.XX	X	XX	X	X	XX	X	X	XX	X

**Programmer Note:** Table 14.3.5.6 will not include timepoints that are summarized in PD endpoint tables in 14.2.

Note: 0.25 mg/kg: Single IV Infusion of 0.25 mg/kg xisomab 3G3  
 0.5 mg/kg: Single IV Infusion of 0.5 mg/kg xisomab 3G3  
 Placebo = pooled placebo  
 N = Within Normal Range, L = Below Normal Range, H = Above Normal Range  

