| | Hours → | | start | end | start | end | start |
| Safety Evaluations | | | | | | | |
| Abbreviated Physical Examination ^{e:} | | | | | | | X ^{r:} |
| Weight | | X ^{f:} | X ^{g:} | X ^{f:} | X ^{g:} | X ^{f:} | X ^{g:} |
| 12-Lead Safety ECG | | | | | | | X ^{r:} |
| Vital Signs (HR, BP, RR, and T) | | X ^{f:} | | X ^{f:} | | X ^{f:} | X ^{r:} |
| Bleeding of Access Site | | | | | | | X ^{g:} |
| Hem, Serum Chem ^{h:} , and UA ^{i:} | | | | | | | X ^{r:} |
| Coagulation ^{j:} | | | | | | X ^{f:} | X ^{g:} |
| Platelet Count ^{s:} | | | | | | X ^{f:} | X ^{g:} |
| Serum Pregnancy Test (♀ only) | | | | | | | X ^{r:} |
| AE Monitoring | | | | X | | | X |
| ConMeds Monitoring | | | | X | | | |
| Study Drug Administration / PK/PD/Immunogenicity | | | | | | | |
| Blood for free xisomab 3G3 PK | | | | | | | X ^{r:} |
| Blood for free xisomab 3G3 PD (aPTT) ^{s:} | | X ^{o:} | | X ^{o:} | | | |
| Blood for Immunogenicity | | | | | | | X ^{r:} |
| Other Procedures | | | | | | | |
| Blood BUN and Potassium (for Kt/V and URR) | | | | | | X ^{f:} | X ^{g:} |
| Dialysate Analysis | | | | | | X ^{k:} | X ^{k:} |
| Visual Assessment and Processing of Dialyzer Membrane | | | | | | | X ^{l:} |
| Return Visits | | | X | | X | | X |

- a: For details on Procedures, refer to [Section 13](#)
- b: Within 28 days prior to Day -8.
- c: Patients will be admitted to the CRU on Day -8, at the time indicated by the CRU and will remain confined up to Day 6 or prior early termination.
- d: Patients will undergo hemodialysis 3 times a week, on Day -7, Day -5, Day -3, and Day 1, Day 3, Day 5, Day 8, Day 10, and Day 12. For each patient, the hemodialysis will last at least 3 hours as per patient standard schedule which will be the same throughout the study.
- e: Symptom-driven physical examination may be performed at other times, at the PI's or designee's discretion.
- f: To be performed ~ 1 hour prior to the start of hemodialysis.
- g: To be performed at the end of hemodialysis.
- h: Samples for serum chemistry will be obtained following a fast of at least 4 hours, however, in case of dropouts or rechecks, patients may not have fasted for 4 hours prior to the serum chemistry sample is taken.
- i: For anuric patients, urinalysis may not be performed.
- j: Coagulation parameters (activated partial thromboplastin time [aPTT], prothrombin time [PT], and international normalized ratio [INR]).

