8.4.2 Rationale for the Dose Selection

Doses of 0.25 mg/kg and 0.5 mg/kg were selected for this phase 2 study in order to provide adequate PD and PK characterization but still allowing a safety margin should the results differ in this population compared to healthy subjects. The 0.25 mg/kg xisomab 3G3 dose is 2.5-fold higher than the lowest dose in the FIH study. The 0.1 mg/kg dose in the FIH study had a short and modest, yet detectable PD effect (several seconds of temporal aPTT prolongation). The 0.25 mg/kg dose is expected to provide an initial plasma concentration that is within the range of average FXI concentration, the molecular target of xisomab 3G3, in human subjects, and may approach saturation in some individuals after full distribution. Therefore, it has the potential to exert brief pharmacological (anti-inflammatory, antithrombotic) activity, possibly lasting up to a day, until elimination of the antibody and hepatic FXI secretion that neutralizes the antibody.

The 0.5 mg/kg dose was safely administered in the FIH study and allowed adequate characterization of the PK profile in healthy adults. In addition, following a 0.5 mg/kg a prolongation of aPTT was seen, with highest values measured at 24 hours postdose and having a sustained effect for at least 72 hours postdose. The 0.5 mg/kg xisomab 3G3 dose is expected to provide, after complete distribution, a plasma concentration that is approximately twice the average human plasma concentration of the FXI antigen. Therefore, this dose is expected to be overcome by FXI generation later, and have pharmacological activity that lasts longer than the lower dose level.

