### 2.2 Endpoints

#### Primary outcome measures:

- The safety and tolerability of xisomab 3G3 will be evaluated versus pre-treatment and placebo by reviewing number and severity of adverse events and use of concomitant medications, physical examination, vascular access site reaction, bleeding time, and changes in vital signs, ECGs, and clinical laboratory evaluations.

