## 7.2 Data Summarization and Presentation of PD Parameters

### 7.2.1 aPTT

**Sample Collection:** Samples for the coagulation parameter (aPTT) will be collected at screening, pre- and post-dialysis on Days -7, -5, -3, 1, 3, 5, and 12. Additional samples for aPTT will be collected following xisomab 3G3/placebo dosing on Day 1 at predose (hour 0, at least 1 hour prior the start of HD session) and at 0.167, 0.5, 1, 2, 3, 4, 6, 8, 12, 16, 24, 48, 96, 120, 144, and 192, hours after xisomab 3G3 start of infusion.

**Baseline Calculation Method Following Day 1 Dosing:** Following xisomab 3G3 dosing on Day 1, aPTT change from baseline will be calculated by dividing postdose aPTT values from average of pre-dose baseline (the average of pre-dialysis aPTT values on Days -7, -5, -3, and 1 will be calculated as pre-dose baseline).

**Fold change in aPTT values:** The fold change in aPTT values on Days -7, -5, -3, 1 (only pre- and post-dialysis aPTT values on Day 1), 3, 5, and 12 will be calculated by dividing the post-dialysis aPTT/pre-dialysis aPTT values for each day separately.

aPTT values will be extracted from the clinical laboratory database and descriptive statistics will be generated using SAS® version 9.3 or higher. Following Day 1 xisomab 3G3 dosing, a table will be presented for the aPTT change from baseline with descriptive statistics.

aPTT values will be listed and summarized by treatment and time points in Tables and Figures for all subjects in the Safety Population (2 active dose levels and pooled placebo). aPTT values will be presented with the same level of precision as received from the clinical laboratory database. Summary statistics, including n, Mean, SD, CV%, SEM, minimum, median, and maximum will be calculated for all nominal values time points. Excluded subjects will be included in the aPPT values tables, but will be excluded from the summary statistics and noted as such in the tables.

Mean and individual aPTT values-time and change from baseline-time profiles will be presented on linear scale. Linear mean plots will be presented with and without SD.

The level of precision for the aPPT values summary statistic will be presented as follows:

- minimum/maximum: in same precision as in the clinical laboratory database
- Mean/median: in one more level of precision than minimum/maximum
- SD/SEM: in one more level of precision than Mean/median
- n will be presented as an integer
- CV% will be presented to the nearest tenth

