## **8.4 Clinical Laboratory Tests (Serum Chemistry, Hematology, Coagulation and Urinalysis)**

Safety serum chemistry, hematology and urinalysis tests are performed at Screening, Day -8 check-in, Day 1 predose, Day 6 and Day 12. For anuric patients, urinalysis may not be performed. Platelet count are collected at start and end of HD on Days -7, -5, -3, 1, 3, 5 and 12 and on Day 6. Platelet count are collected at start and end of HD on Days -7, -5, -3, 1, 3, 5 and 12 and Day 6. aPTT results are presented and discussed in the PD Section 7.2.

Out-of-range values and clinically significant results will be listed.

For all numeric laboratory values, descriptive statistics will be presented for each laboratory test by assessment time point and treatment. Change from baseline will be summarized in a similar manner. Baseline is defined as the result closest and prior to

dose which may include unscheduled results. This will typically be the result collected at predose on Day 1. Postdose unscheduled events or early termination results will not be included in summaries.

For each laboratory test, a shift table will be developed to compare the frequency of the results at baseline (above normal, normal, or below normal) with the respective postdose results.

Coagulation parameters and platelet count will be listed and presented together since they have the same timepoints. Urinalysis test results will be listed only.

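### Table 14.3.5.5 programs PT/INR change from baseline as a same-day post/pre-dialysis ratio, so after Day 1 the column is not the comparison with the pre-dose value that its footnote describes

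*SAP*

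**What the plan says.** Tables 14.3.5.1, 14.3.5.3 and 14.3.5.5 share one shell in SAP 11.3, with a change-from-baseline block whose asterisk leads to the footnote "Baseline is defined as the result closest and prior to dose on Day 1". Directly below it a programmer note makes an exception: "for PT, INR and PT/INR, the pre-dialysis value will be the baseline value for that day". It equates the change with the post-dialysis value over the pre-dialysis value.

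SAP 8.4 covers every numeric laboratory test and makes no such exception: "Change from baseline will be summarized in a similar manner. Baseline is defined as the result closest and prior to" the dose, and "This will typically be the result collected at predose on Day 1". The footnote to the shift tables, including 14.3.5.6 for coagulation, repeats the pre-dose definition. Protocol 14.3.1 plans summaries of the difference to baseline, where appropriate, for quantitative safety data. SAP Section 9 mentions only the length of dialysis and its sampling time, and otherwise declares the analyses aligned with the protocol.

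For aPTT, SAP 7.2.1 provides two separate measures. One is against pre-dose values ("aPTT change from baseline will be calculated by dividing postdose aPTT values from average of pre-dose baseline"); the other is a same-day post/pre fold change. PT and INR have only the second as a tabulated change.

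**The concern.** Two incompatible definitions are attached to one column. The primary outcome in SAP 2.2 states: "The safety and tolerability of xisomab 3G3 will be evaluated versus pre-treatment and placebo", and changes in laboratory evaluations are part of it. A same-day ratio answers a different question, namely what the dialysis session did to the clotting time that day. After Day 1 both halves of the ratio are post-dose, so a shift present since dosing drops out and the column reads near 1.0 under a footnote saying it is measured from before the dose.

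Table 14.3.5.5 also holds platelet counts, to which the note does not apply. The same column would therefore carry a change from the pre-dose baseline for one test and a session ratio for the others. Tables 14.3.5.5 and 14.3.5.6 would use the word baseline differently for the same PT result.

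**Working it through.** The plan states no figure on this point, so the check is a count of scheduled results under each rule.

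**Inputs.** Coagulation draws come from the flow chart (Protocol Section 6). SAP 8.4 agrees with it, since coagulation shares the platelet time points: start and end of dialysis on Days -7, -5, -3, 1, 3, 5 and 12, plus Day 6. Dialysis takes place "on Day -7, Day -5, Day -3, and Day 1, Day 3, Day 5, Day 8, Day 10, and Day 12", so not on Day 6.

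**Count.** 7 days × 2 + 1 = 15 on-study draws. Pre-dose: 3 × 2 + 1 (Day 1 pre) = 7. Post-dose: 15 − 7 = 8. Protocol Table 4 lists 16 on-study coagulation draws; the schedule gives 16 only if screening is counted. I use the schedule.

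**Each post-dose result under the two rules.**

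| Result | Programmer note | Footnote and SAP 8.4 |
|---|---|---|
| Day 1 post | ÷ Day 1 pre (pre-dose) | vs last pre-dose |
| Day 3 pre | no change value | vs last pre-dose |
| Day 3 post | ÷ Day 3 pre (post-dose) | vs last pre-dose |
| Day 5 pre | no change value | vs last pre-dose |
| Day 5 post | ÷ Day 5 pre (post-dose) | vs last pre-dose |
| Day 6 | no ratio possible | vs last pre-dose |
| Day 12 pre | no change value | vs last pre-dose |
| Day 12 post | ÷ Day 12 pre (post-dose) | vs last pre-dose |

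Under the note, 1 result has a pre-dose comparison, 3 have a post-dose denominator and 3 have no change value: 3 + 3 = 6 without a pre-dose comparison. Day 6 makes it 7 of 8 if the note is taken to govern all PT/INR rows. It stays at 6 of 8 if Day 6 falls back on the footnote. Under the footnote rule, 8 of 8 are compared.

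**Why a sustained shift cancels.** Let b be the pre-dose level, k a lasting multiplicative shift after dosing, and s the effect of a session.

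- Day 1 ratio: (k·b·s) / b = k·s.
- Day 3, 5 or 12 ratio: (k·b·s) / (k·b) = s. The shift k is gone.
- Day 3, 5 or 12 pre-dialysis result minus baseline: k·b − b = b(k − 1), with no same-day session effect.

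With assumed values k = 1.2 and s = 1, the note gives 1.2 on Day 1 and 1.2/1.2 = 1.0 on Days 3, 5 and 12, whereas the ratio to the pre-dose value is 1.2 throughout. Assumed shifts of 1.1 and 1.5 also read 1.0 on those days. The pre-dialysis results, which would show a lasting shift free of the same-day session, are the ones given no change value.

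**Day 6 in the in-text tables.** The shell shared by Tables 11-6 and 12-2 to 12-4 (SAP 11.1) has a Day 6 row with pre-dialysis, post-dialysis and fold-change cells. With no dialysis that day, it cannot be filled as drawn.

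**The case against.** The note looks deliberate. Tables 12-2 to 12-4 are titled as pre- versus post-dialysis comparisons, run from Day -7 to Day 12 and take Table 14.3.5.5 as their source. Session ratios before dosing therefore sit beside those after dosing, with placebo alongside, which is a legitimate comparison of the session effect. That stands, and is why the ratio should be kept. It does not justify naming it change from baseline under a contrary footnote, and it does not show a sustained shift.

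Protocol 14.3 also allows the SAP to modify planned analyses, and the protocol's difference to baseline is qualified as where appropriate. But SAP 8.4 itself adopts the pre-dose rule for all numeric tests, and Section 9 records no exception.

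Three stronger inferences are tempting, and the documents support none of them.

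- *That the pre-dose comparison is lost from the report.* Observed values with a baseline row, Table 14.3.5.6 on the pre-dose baseline and out-of-range Table 14.3.4.2 remain. Appendix 16.2.8.1.3 lists every coagulation result, so with at most 24 patients each individual change can be rebuilt.
- *That the column would hide a known drug effect.* The documents report prolongation of aPTT and no PT/INR effect. The nearest support is borrowed from aPTT at 0.5 mg/kg in healthy subjects, described as "having a sustained effect for at least 72 hours postdose", which covers the Day 3 denominator at (3 − 1) × 24 = 48 nominal hours. For 0.25 mg/kg, Protocol 8.4.2 expects activity for possibly up to a day.
- *That whole time points vanish for PT/INR and platelets*, because notes on Tables 14.3.5.5 and 14.3.5.6 omit time points already summarised in Section 14.2. SAP 8.4 sends only aPTT to the PD section, and emptying Table 14.3.5.5 would defeat its role as source for Tables 12-2 to 12-4. Loose wording is the likelier explanation.

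Shells are also declared to show general layout only, which softens the Day 6 point. The programmer note is different: it is a specific calculation rule.

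**Conclusion.** The contradiction is real and the column is wrong for its stated purpose after Day 1. Of 8 scheduled post-dose PT/INR results, 1 is compared with a pre-dose value; 6 or 7 are not, depending on how Day 6 is treated. The count assumes the flow-chart schedule and complete data.

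The consequence is modest. This is a descriptive safety column, the sample size was set without statistical considerations, and the underlying values are reported elsewhere. What is missing is a tabulated continuous within-patient change from pre-dose for PT and INR after Day 1, which SAP 8.4 promises. It should be corrected, since a reader who trusts the footnote would take a value near 1.0 as evidence of no change since dosing.

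**What to change.** 1. Replace the same-day baseline note. In Table 14.3.5.5 report PT, INR and PT/INR change as the difference from the last result before the Day 1 dose, at all 8 post-dose time points including Day 6. Label pre- and post-dialysis rows, because post-dialysis values also carry the session effect.
2. Keep post-dialysis over pre-dialysis in its own column, headed as a same-day fold change, for dialysis days only, as the source for Tables 12-2 to 12-4. In that in-text shell show Day 6 as a single value.
3. As a minor clarification, reword the omission notes on Tables 14.3.5.5 and 14.3.5.6 so that they exclude aPTT only, because it is summarised in Section 14.2.

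The cost is three note edits, one added column and one corrected shell row. No new samples or visits are needed; the only drawback is a wider Table 14.3.5.5.

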 # = Lowest of the lower ranges and highest of the higher ranges are used. Refer to Appendix 16.1.10.1 for the breakdown.  
 \* Baseline is defined as the result closest and prior to dose on Day 1.

Program: /AAXXXXX/ECR/sas\_prg/stsas/tab\_PROGRAMNAME.sas DMMYYYY HH:MM

Table 14.3.5.7 Vital Sign Summary and Change from Baseline (Safety Population)

Vital Sign(unit)	Time Point	Statistic	Change from Baseline*					
			0.25 mg/kg	0.5 mg/kg	Placebo	0.25 mg/kg	0.5 mg/kg	Placebo
XXXXXXXXX (unit)	Screen	n	XX	XX	XX			
		Mean	X.XX	X.XX	X.XX			
		SD	X.XXX	X.XXX	X.XXX			
		Minimum	X.XX	X.XX	X.XX			
		Median	X.X	X.X	X.X			
		Maximum	XX.X	XX.X	XX.X			
		<Also include Days -7, -5 and -3>						
Baseline*		n	XX	XX	XX			
		Mean	X.XX	X.XX	X.XX			
		SD	X.XXX	X.XXX	X.XXX			
		Minimum	X.XX	X.XX	X.XX			
		Median	X.X	X.X	X.X			
		Maximum	XX.X	XX.X	XX.X			
		Day X, Hour X.XX		n	XX	XX	XX	XX
Mean	X.XX			X.XX	X.XX	X.XX	X.XX	X.XX
SD	X.XXX			X.XXX	X.XXX	X.XXX	X.XXX	X.XXX
Minimum	X.XX			X.XX	X.XX	X.XX	X.XX	X.XX
Median	X.X			X.X	X.X	X.X	X.X	X.X
Maximum	XX.X			XX.X	XX.X	XX.X	XX.X	XX.X
<include all postdose timepoints>								

Note: 0.25 mg/kg: Single IV Infusion of 0.25 mg/kg xisomab 3G3  
 0.5 mg/kg: Single IV Infusion of 0.5 mg/kg xisomab 3G3  
 Placebo = pooled placebo  
 \* Baseline is defined as the result closest and prior to the dose on Day 1.

Program: /AAXXXXX/ECR/sas\_prg/stsas/tab\_PROGRAMNAME.sas DDMMYYYY HH:MM

Table 14.3.5.8 12-Lead Electrocardiogram Summary and Change from Baseline (Safety Population)

Measurement (unit)	Time Point	Statistic	Change from Baseline*					
			0.25 mg/kg	0.5 mg/kg	Placebo	0.25 mg/kg	0.5 mg/kg	Placebo
XXXXXXXX (unit)	Screen	n	XX	XX	XX			
		Mean	X.XX	X.XX	X.XX			
		SD	X.XXX	X.XXX	X.XXX			
		Minimum	X.XX	X.XX	X.XX			
		Median	X.X	X.X	X.X			
		Maximum	XX.X	XX.X	XX.X			
	Baseline*	n	XX	XX	XX			
		Mean	X.XX	X.XX	X.XX			
		SD	X.XXX	X.XXX	X.XXX			
		Minimum	X.XX	X.XX	X.XX			
		Median	X.X	X.X	X.X			
		Maximum	XX.X	XX.X	XX.X			
	Day X, Hour X.XX	n	XX	XX	XX	XX	XX	XX
		Mean	X.XX	X.XX	X.XX	X.XX	X.XX	X.XX
		SD	X.XXX	X.XXX	X.XXX	X.XXX	X.XXX	X.XXX
		Minimum	X.XX	X.XX	X.XX	X.XX	X.XX	X.XX
		Median	X.X	X.X	X.X	X.X	X.X	X.X
		Maximum	XX.X	XX.X	XX.X	XX.X	XX.X	XX.X

<include all postdose timepoints>

Note: 0.25 mg/kg: Single IV Infusion of 0.25 mg/kg xisomab 3G3

0.5 mg/kg: Single IV Infusion of 0.5 mg/kg xisomab 3G3

Placebo = pooled placebo

\* Baseline is defined as the result closest and prior to the dose on Day 1.

Program: /AAXXXX/ECR/sas\_prg/stsas/tab\_PROGRAMNAME.sas DDMMYYYY HH:MM

Tables 14.2.12 will be in the following format:

Table 14.5.5.9 Frequency of Immunogenicity - ADA Titer (Safety Population)

Day	0.25 mg/kg Xisomab 3G3		0.5 mg/kg Xisomab 3G3		Pooled Placebo	
	Positive	Negative	Positive	Negative	Positive	Negative
Day 1	X (%)	X (%)	X (%)	X (%)	X (%)	X (%)
Day 12	X (%)	X (%)	X (%)	X (%)	X (%)	X (%)

Note: % is percentage of total subject dosed in each treatment.

Program: /AAXXXXX/ECR/sas\_prg/stsas/tab\_PROGRAMNAME.sas DDMMYYYY HH:MM

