9.2 Endpoints

Primary outcome measures:

- The safety and tolerability of xisomab 3G3 will be evaluated versus pre-treatment and placebo by reviewing number and severity of adverse events and use of concomitant medications, physical examination, vascular access site reaction, bleeding time, and changes in vital signs, ECGs, and clinical laboratory evaluations.

Secondary outcome measures:

- PD using dose-dependency of drug potency, determined by measuring changes in coagulation parameters, and thrombus accumulation (assessed and ranked by visual inspection) within the dialyzer cartridges and total protein accumulation in the HD filter after xisomab 3G3-treatment versus pre-treatment and placebo.
- Efficacy on hemodialysis efficiency using BUN and potassium levels before and after hemodialysis, length of HD, measurement of urea removed by 3 hours of dialysis, and total dialysate urea (single pool Kt/V and URR) after xisomab 3G3-treatment versus pre-treatment and placebo.

Other outcome measures:

- PK parameters of xisomab 3G3, calculated, as appropriate: AUC0-t, AUC0-inf, AUC%extrap, Cmax, Tmax, Kel, t^{1/2}, CL, and Vss.
- Development of immunity or antibodies against xisomab 3G3 after drug exposure.

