14.3.1 Safety and Tolerability Analyses

All safety data will be populated in the individual CRFs. All safety data will be listed by patients.

The placebo patients from all cohorts will be pooled into a single placebo group for all summaries and presentations

Dosing dates and times will be listed by patient.

Incidence and time of bleeding from the HD access sites on the AV fistula (or AV graft), as described in [Section 13.2.6](#), will be counted and recorded. Treatment versus pre-treatment, placebo, and post-treatment results will be compared.

AEs will be coded using the most current version of Medical Dictionary for Regulatory Activities (MedDRA®) available at Celerion and summarized by treatment (2 active dose levels and pooled placebo) for the number of patients reporting the treatment emergent adverse event (TEAE) and the number of TEAEs reported. A by-patient AE data listing including verbatim term, coded term, treatment, severity, and relationship to study drug will be provided.

Safety data including ECGs, vital signs assessments, clinical laboratory results and vascular access site reaction, will be summarized by treatment (2 active dose levels and pooled placebo) and point of time of collection.

Descriptive statistics using appropriate summary statistics will be calculated for quantitative safety data as well as for the difference to baseline, when appropriate. In addition, a shift table describing out of normal range shifts will be provided for clinical laboratory results.

Concomitant medications will be listed by patient and treatment (2 active dose levels and pooled placebo) and coded using the most current version of WHO drug dictionary available at Celerion. Medical history will be listed by patient.

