Appendix 16.1.10.1 Clinical Laboratory Reference Ranges

Laboratory Group	Test Name	Sex	Age Category	Reference Range	Unit
Serum Chemistry	Test Name	XXXXXX	XX	XX - XX	units
	Test Name	XXXXXX	XX	XX - XX	units
	Test Name	XXXXXX	XX	XX - XX	units
	Test Name	XXXXXX	XX	XX - XX	units
	Test Name	XXXXXX	XX	XX - XX	units
	Test Name	XXXXXX	XX	XX - XX	units
Hematology	Test Name	XXXXXX	XX	XX - XX	units
	Test Name	XXXXXX	XX	XX - XX	units
	Test Name	XXXXXX	XX	XX - XX	units
	Test Name	XXXXXX	XX	XX - XX	units
	Test Name	XXXXXX	XX	XX - XX	units

<similar for remaining Laboratory Groups and Test Names>

Program: /CAXXXXX/sas\_prg/stsas/lis\_PROGRAMNAME.sas DDMMYYYY HH:MM

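### The laboratory shift-table footnote, read literally, sets the low/normal/high cut-offs to the widest range across sex and age, and the SAP gives no other rule

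*SAP*

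**What the plan says.** Protocol 14.3.1 promises that "a shift table describing out of normal range shifts will be provided for clinical laboratory results". SAP 8.4 repeats the plan: for each test, "a shift table will be developed to compare the frequency of the results at baseline" with the postdose results, in three classes (above, within and below normal). Neither section says which range defines normal.

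The shells in SAP 11.3 give more detail. One shell serves shift Tables 14.3.5.2 (serum chemistry), 14.3.5.4 (hematology) and 14.3.5.6 (coagulation and platelets). Its notes define the classes as "N = Within Normal Range, L = Below Normal Range, H = Above Normal Range" and then add, against a # mark, "Lowest of the lower ranges and highest of the higher ranges are used", with a pointer to an appendix for the detail. The appendix named there, "Appendix 16.1.10.1 Clinical Laboratory Reference Ranges", is laid out in SAP 12 with columns for sex and age category.

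The same # note stands under the shell for summary Tables 14.3.5.1, 14.3.5.3 and 14.3.5.5. In that shell # is attached to the entry in the Reference Range column.

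**The concern.** In the summary tables the note explains why one printed range stands for several, which is harmless. The shift shell has no range column and no # in its body. Its only use of a range is to sort results into L, N and H, so a programmer who follows the note literally would apply the combined range as the cut-offs. SAP 1 says that the table-shell section describes how outputs trace back to the data, so shells can be expected to guide programming.

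Laboratory results are one component of the primary outcome measure, which includes "changes in vital signs, ECGs, and clinical laboratory evaluations" (Protocol 9.2). The shift tables are the only planned by-treatment count of laboratory results by normal or abnormal class. Each group will mix patients whose own ranges may differ: Protocol 10.1 aims for at least 50% women per cohort, and Protocol 11.1 admits ages 18 to 80.

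**Working it through.** The plan states no figure on this point, so there is none to reproduce. The check has four steps.

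**1. Which range is used where**

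| Display | Range printed? | Combined-range note? | What a range does there |
|---|---|---|---|
| Summary Tables 14.3.5.1, .3, .5 | Yes, marked # | Yes | Display only |
| Shift Tables 14.3.5.2, .4, .6 | No | Yes, # not anchored | Sets L/N/H |
| Out-of-range Tables 14.3.4.1 to 14.3.4.3 | Yes, in column heads | No | Sets H/L flags |

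If the flags in the third row use the patient's own range, a result flagged L or H there could be counted as N in the shift table of the same report.

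**2. What the combined range does to a shift**

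Let *a* be the patient's own lower limit and *c* the combined lower limit, with *c* below *a*. The band is the interval from *c* up to *a*. Upper limits work as a mirror image.

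| Baseline | Postdose | Own range | Combined range | Effect |
|---|---|---|---|---|
| At or above *a* | In band | N to L | N to N | Real fall hidden |
| In band | At or above *a* | L to N | N to N | Real recovery hidden |
| In band | Below *c* | L to L | N to L | False fall created |
| Below *c* | In band | L to L | L to N | False recovery created |
| In band | In band | L to L | N to N | No shift either way, wrong cell |

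If *a* = *c*, the band is empty and nothing changes. Only tests with more than one range are affected.

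**3. Hemoglobin as an example**

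Protocol 8.5 and 13.3 give a possible circuit loss of about 228 mL. Assume a starting value of 12 g/dL and a blood volume of 4 to 5 L. The fall is then 12 × 228/5000 = 0.55 g/dL to 12 × 228/4000 = 0.68 g/dL. Take a man who goes from 12 to 12 − 0.55 = 11.45, and assume that the women's limit is the lower one:

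- Men's limit above 11.45 and up to 12, women's limit at or below 11.45: own range N to L, combined range N to N. The shift is hidden.
- Men's limit above 12, women's limit above 11.45 and up to 12: own range L to L, combined range N to L. A shift is created.

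The direction depends on limits that the documents do not give.

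**4. How many patients**

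Group sizes follow from Protocol 14.1 (9 to 12 per cohort, 2:1). Each active dose has 9 × 2/3 = 6 to 12 × 2/3 = 8 patients. Pooled placebo has 2 × 9/3 = 6 to 2 × 12/3 = 8. One patient is therefore 1/8 = 12.5% to 1/6 = 16.7% of a group.

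To illustrate the mechanism, assume a normally distributed test. Let *z* be the position of the own lower limit and *g* the gap between own and combined limits, both in SD units. The share of results that are low by the own range but counted as N is Φ(*z*) − Φ(*z* − *g*). The patient counts assume that half of a group, 3 of 6 or 4 of 8, belongs to the affected sex.

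| *g* | *z* = −1 | *z* = 0 | *z* = +1 | Expected patients per group, test and time point |
|---|---|---|---|---|
| 0 | 0% | 0% | 0% | 0 |
| 0.5 | 9.2% | 19.1% | 15.0% | 0.3 (3 × 0.092) to 0.8 (4 × 0.191) |
| 1 | 13.6% | 34.1% | 34.1% | 0.4 (3 × 0.136) to 1.4 (4 × 0.341) |

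Both *z* and *g* are assumptions. With own-range classification every entry is 0 by definition.

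**The case against.** The strongest reply is that the note is simply a leftover. # is anchored only to the range column of the summary shell, and the notes under the two shells are nearly identical. Copying slips occur elsewhere in these shells: Tables 11-7 and 11-8 head two columns with the 0.25 mg/kg dose, Table 14.3.1.1 gives the doses in mcg/kg, and the immunogenicity shell carries a number that does not match the table list. SAP 11 says that the shells show general layout and may change. This stands: the documents do not establish that the shift tables will be classified by the combined range. It does not remove the need for a correction, because the note would still tell a reader of the report that the combined range was used.

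The second reply is that other displays cover the consequence, and it also stands. Out-of-range values are listed by patient with H/L and clinical-significance flags. Numeric change from baseline is summarized by treatment with minimum and maximum, without reference to any range. Abnormal laboratory findings can be adverse events (Protocol 13.2.8.1), which are tabulated by treatment. No decision rule uses the shift counts.

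A reader might also infer a one-way bias, in which the widest range can only hide abnormality. That is true of a single result, which can only move into N. It is not true of a shift, which compares two results: rows three and four of the second table above are false shifts.

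**Conclusion.** The point holds as an unanchored footnote that, taken literally, is the only range instruction for the three shift tables and would misclassify results for any test with more than one range. The error can go in either direction.

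Its size is unknown. The appendix shell is blank, so it shows neither which tests have several ranges nor how far apart the limits lie. Under the assumed values above, up to about one patient per group, test and time point could be affected; for tests with a single range, none would be.

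Two stronger conclusions are not supported. One is that abnormal values will be counted as normal; that treats one reading of the note as settled. The other is that a primary safety result is compromised. Laboratory change is one of several components of the primary outcome, the analysis is descriptive, and the displays named above would still show a marked hemoglobin fall or enzyme rise. This is a minor to moderate correction.

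**What to change.** In the notes to Tables 14.3.5.2, 14.3.5.4 and 14.3.5.6, replace the # footnote with: *Each result is classified L/N/H against the reference range for that patient's sex and age (Appendix 16.1.10.1).* Keep the combined range only as the displayed range in Tables 14.3.5.1, 14.3.5.3 and 14.3.5.5.

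The cost is one footnote in a shared shell, changed before database lock and unblinding. It needs no new data or analysis, since the ranges by sex and age are already planned as a listing. If the sponsor does intend the combined range for classification, the SAP should say so in Section 8.4 and justify it.
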